Study Protocol

Project Title:

Version Date:

Skeletal muscle atrophy and dysfunction following total knee arthroplasty

3-23-22

NCT number:

NCT03051984

**Principal
Investigator
(contact):**

[name]

Grant Sponsor:

NIA R01 AG050305

PROTOCOL SUMMARY

Knee osteoarthritis (OA) is the leading cause of disability in older adults. Because non-surgical therapies are inadequate in managing symptoms and do not alter the disease course, total knee arthroplasty (TKA) is an important final treatment option. While TKA alleviates joint pain, objectively-measured physical function does not improve much beyond pre-surgical levels. Moreover, it often takes 1-2 years to recover to function to pre-surgical levels. TKA fails to correct disability, in part, because of the precipitous decline in lower-extremity neuromuscular function in the early, post-surgical period, forcing patients to first overcome the disabling effects of the procedure before redressing pre-surgery functional deficits. Surprisingly, very little is known about the nature of muscle structural and functional adaptations during the early, post-surgical period, aside from a small number of studies at the whole muscle level suggesting decreased neural activation as the major cause of dysfunction. To address these gaps in scientific knowledge and clinical treatment options early following TKA, our goals in this project are to: 1) to comprehensively examine, from the molecular to the whole body level, skeletal muscle structural and functional adaptations following TKA and 2) to assess the utility of neuromuscular electrical stimulation (NMES) to counter early, post-surgical muscle adaptations. Based on our preliminary data, we hypothesize that TKA causes profound reductions in skeletal muscle size and intrinsic function during the early, post-surgical period that contribute to long-term functional disability and that these adaptations can largely be prevented by NMES. To accomplish our goals, we will study patients with advanced-stage knee OA prior to and 5 following surgery who are randomized to receive NMES or no intervention during this period. All volunteers will receive standard of care physical rehabilitation during this period. Tissue acquired from skeletal muscle biopsies will be used to characterize skeletal muscle myofilament and mitochondrial structure and function, in combination with assessments of whole muscle and body functional capacity. If successful, our results could shift conventional thinking in this field away from the role of neural adaptations as a cause of post-surgical disability and emphasize the importance of muscle atrophy and intrinsic myofilament function. Additionally, our data on the utility of NMES to prevent such adaptations may provide important mechanistic data to support this modality as a new transitional rehabilitative care intervention to improve long-term functional prognosis in TKA recipients.

PURPOSE AND OBJECTIVES

Knee OA is the leading cause of disability in older adults (1). Because non-surgical therapies are inadequate in managing symptoms (2) and do not alter the disease course, TKA is an important treatment option for knee OA. It is currently the most common elective surgery in the US (3) and its use will rise dramatically (~5-fold) in the future, to ~3.5 million surgeries/yr by 2030 (4) with the expansion of the elderly population. While TKA improves patient-reported function by alleviating joint pain (5), objectively-measured physical function does not improve much beyond pre-surgical levels, which is already severely impaired (6-8), and does not reach healthy control levels even years after surgery (8-11). The inability of TKA to correct functional deficits consigns a large number of older adults to continued disability and greater risk for progression to severe disability (12-14).

TKA fails to correct disability, in part, because of the precipitous decline in lower-extremity neuromuscular function in the early, post-surgical period (8, 15, 16), forcing patients to first overcome the disabling effects of the procedure before redressing pre-surgery functional deficits (6-8). Surprisingly, very little is known about the nature of muscle structural and functional adaptations during the early, post-surgical period, aside from a small number of studies at the whole muscle level (15, 16). Although informative, these studies are unable to define the mechanisms underlying reduced function because of the imprecision of measurements at this anatomic level and the multitude of physiological systems and subjective factors that impact whole muscle function. While the need for early intervention post-TKA to forestall its disabling effects has been consistently recognized (17, 18), there are no widely-accepted, evidence-based interventions that target this early functional decline. We believe that lack of knowledge of the determinants of TKA-induced functional decline and therapeutic interventions to prevent or correct these maladaptations represent critical barriers to more effectively recover physical function in TKA recipients.

The proposed studies address these barriers and their successful completion would advance knowledge of early, post-TKA skeletal muscle adaptations at the cellular, organellar and molecular levels, providing a mechanistic evidence base to inform the development of preventive and rehabilitative interventions. As these muscle deficits contribute to long-term disability in TKA recipients (15, 19, 20), beneficial effects of NMES would highlight its potential as a transitional intervention to bridge a gap in rehabilitative care during the early, post-surgical period. Moreover, as NMES is inexpensive, FDA approved, portable to the clinic and home settings and there are clinicians trained in its use (PTs/OTs), financial, logistical and regulatory barriers for its broader application would be minimal. Finally, beneficial effects of NMES may argue for its broader application to other orthopedic surgical populations that experience post-surgical functional morbidities (21, 22), as well as other older adult populations that suffer muscle atrophy and dysfunction during acute disabling events (14, 23).

Background and Hypothesis for Aim 1

Effects of TKA on skeletal muscle structure and function. Physical function declines rapidly and profoundly in the early, post-surgical period following TKA (8, 24). One determinant of the TKA-related reduction in physical function is lower extremity muscle weakness (15, 16, 25). Data from our labs and others show that reductions are most prominent in the quadriceps, where strength declines >50% early, post-surgery (15, 25-27). Conventional wisdom holds that deficient neural activation is the primary factor driving muscle weakness, with a much smaller contribution from intrinsic muscle adaptations, such as atrophy (15). However, studies at the whole muscle level are insufficient to define muscle-specific adaptations because of methodological limitations (eg, whole muscle imaging techniques underestimate muscle atrophy compared to single fiber assessments) and confounding factors (eg, impaired neural activation and antagonist muscle co-contraction impair whole muscle strength measures). Regarding the latter, using single muscle fibers, we have shown, for the first time, profound (~30-50%) deficits in contractility early following TKA at the cellular level, including reductions in tension (ie, force/CSA) and velocity in MHC IIA and IIX fibers. Such contractile deficits likely contribute to whole muscle/body functional deficits, as MHC II fibers are important determinants of dynamic muscle function (28).

Muscle size and function are intimately related to cellular energy metabolism (29, 30). Alterations in mitochondrial content, structure and function that alter protein anabolism/catabolism (31, 32) and/or production of metabolites, such as reactive oxygen species (ROS), have been shown to promote atrophy and contractile dysfunction (33-36). Stimuli present in the perioperative and early, post-surgical period, such as inflammation, hypoxia and muscle disuse, can provoke mitochondrial loss and dysfunction and, in turn, muscle atrophy and weakness (35, 37, 38). Thus, mitochondria may serve to both sense these stimuli and transduce their signal throughout the cell. In this context, the early, post-TKA period is characterized by detrimental mitochondrial adaptations that may not only impair energy provision to support physical function (39, 40), but may contribute to muscle atrophy and dysfunction (33, 38, 41). Collectively, available literature and our preliminary data in TKA recipients suggest that it is reasonable to hypothesize that: *TKA will reduce single skeletal muscle fiber size and contractility and mitochondrial content and function, while increasing mitochondrial ROS generation.*

Background and Hypothesis for Aim 2

Effects of NMES on skeletal muscle structure and function following TKA. During the early, post-surgical period, rehabilitation of TKA recipients is impeded by pain, healing of the surgical site and limited range of motion. Because of these impediments, more anabolic/strengthening exercises are not started until several weeks post-surgery. NMES has been forwarded as an adjunct to classical resistive-type exercises begun at this later date to overcome neural activation deficits to allow activation of a greater quantity of muscle mass (42). A recent trial, which has been the largest to date using NMES in TKA recipients, showed that NMES as an adjunct to resistance training, with both starting at 4 weeks post-surgery, had no additional benefit over resistance training alone (43), a result confirmed in other orthopedic surgical populations (44). In stark contrast to these results, use of NMES alone early, post-TKA improves physical function (45). In fact, work from our labs showed that NMES begun 48 hrs post-surgery and maintained for 6 wks reduced quadriceps strength loss and lessened reductions in physical function (46). The timing of the start of the NMES intervention is critical because, although we acknowledge that use of NMES in orthopedic populations is not new, its use early post-surgery is. More specifically, NMES use early post-surgery to counter skeletal muscle atrophy and intrinsic dysfunction

may offer a promising transitional intervention to bridge the gap in rehabilitation care and improve long-term muscle functionality.

For NMES to improve disability in TKA recipients, it should address the mechanisms underlying persistent functional deficits. While impaired neural activation is widely believed to drive early, post-surgical reductions in muscle strength (15), these deficits regress rapidly, with near complete correction within 3-6 months (46). In contrast, intrinsic muscle adaptations are thought to remediate more slowly, contributing disproportionately to long-term functional deficits (15, 19, 20). Thus, while NMES may improve early functional deficits due to impaired neural activation (47, 48), as our data show (46), to impact long-term disability it needs to prevent atrophy and intrinsic contractile dysfunction during the early, post-surgical period. To this end, our preliminary data provide the first direct evidence of effects of NMES on muscle fiber size and function in TKA recipients. We found that early use of NMES diminishes fiber atrophy in MHC I and II fibers and improves myofilament protein function in MHC II fibers, with a surprising improvement in contractile velocity (+23%) after 5 wks. The combined effect of improved tension and velocity may mitigate reductions in whole muscle power output (power= force X velocity) that predispose to disability (49). These effects of NMES on single muscle fiber size and MHC II fiber function, particularly improvements in contractile velocity, which are increasingly thought to be at the root of deficits in muscle power that promote disability (50), may ameliorate the precipitous decline in lower extremity function in the early post-surgical period following TKA.

How does NMES preserve muscle size and function? As NMES maintains neuromuscular activation in the face of post-operative muscle disuse, it likely functions similar to standard exercise, which maintains myocellular size and function during catabolic conditions (51, 52). Several pathways stimulated by exercise influence muscle size/function, in part, by preserving mitochondrial content and function (53-58). In support of this notion, we found that NMES not only preserved skeletal muscle IMF mitochondria, but dramatically increased their content. In addition to these structural effects, NMES nearly prevented TKA-induced reductions in ADP-stimulated, oxygen consumption rate in isolated mitochondria. These effects of NMES on mitochondrial biology may partially explain its ability to mitigate muscle atrophy, in accord with genetic and pharmacological interventions in pre-clincial models that seek to preserve mitochondrial content and function and have been shown to prevent atrophy (33, 35, 59, 60). To our knowledge, however, this hypothesis has never been evaluated in humans, much less over time in response to a clinical events that predispose to disability progression in older adults (14, 23). Collectively, our preliminary data describing the effects of early NMES use following TKA on myofilament and mitochondrial content and function suggest that it is reasonable to hypothesize that: *NMES will diminish TKA-induced single muscle fiber atrophy, declines in contractile and mitochondrial function and increases in ROS production, while increasing mitochondrial content.*

Literature Cited

1. Anonymous. (2009) Prevalence and most common causes of disability among adults--United States, 2005. *MMWR Morbid Mortal Week Rep* **58**, 421-426
2. Turk, D. C., Wilson, H. D., and Cahana, A. (2011) Treatment of chronic non-cancer pain. *Lancet* **377**, 2226-2235
3. Bateman, B. T., Schmidt, U., Berman, M. F., and Bitnner, E. A. (2010) Temporal trends in the epidemiology of severe postoperative sepsis after elective surgery: a large, nationwide sample. *Anesthesiology* **112**, 917-925

Hypothesis: TKA will impair whole body and muscle function, in part, through reductions in skeletal muscle fiber size, with preferential atrophy in MHC II sub-types, reduced single fiber tension (force/CSA) and velocity and decreased mitochondrial content and function.

Aim 2: Define the utility of NMES to prevent early, postsurgical skeletal muscle structural and functional adaptations to TKA.

Hypothesis: NMES will lessen TKA-induced muscle fiber atrophy and contractile dysfunction and preserve or increase mitochondrial content and respiration while lessening mitochondrial ROS production.

METHODS AND PROCEDURES

We will use a randomized, controlled design, in which older adult patients with knee OA being evaluated for TKA will be recruited and undergo baseline evaluations (Pre-surgery Testing) prior to surgery. Patients will then be randomized (1:1) to a 5 week intervention of NMES or control (n=32/group, expecting 25% attrition rate to arrive at n=24/group) using a covariate-adaptive approach, which will incorporate age, BMI, sex and surgeon into the randomization scheme. After completing the intervention, they will be re-tested at 5 weeks (5 wk Post-surgery Testing) following surgery. Volunteers can opt into an optional 2 week follow-up testing period. Primary outcomes will be tested at the 5 week evaluation, with 2 wk testing including assessment of ancillary mechanistic hypotheses. Assessment of physical activity by accelerometry (5 d each throughout the 5 week post-surgical period) will monitor variation in physical activity between groups. Each phase of the protocol is described below.

Pre-surgery testing will include assessments of whole muscle size and function, accelerometry to assess habitual weight-bearing activity level, single muscle fiber size and mechanical function and mitochondrial content and function. Detailed descriptions of these assessments are provided below.

Treatment intervention Volunteers will be randomized to NMES or control groups for the 5 weeks following TKA surgery (described below in detail).

5 wk Post-surgery testing will include measurements identical to Baseline Testing, with post-training biopsies performed ≥ 3 d following strength testing/NMES to eliminate any residual effects, per our usual protocol in our past IRB-approved training studies in other clinical populations (heart failure, end-stage knee osteoarthritis).

2 wk Post-surgery testing (optional) will consist of a skeletal muscle biopsy to assess single muscle fiber size, mitochondrial content and function and anabolic catabolic signaling pathways via standard biochemical/immunolabeling techniques.

6 month Post-surgery testing will include assessments of whole muscle size and function and whole body functional measures to provide data on whether hypothesized preservation in single muscle fiber size/function with NMES will relate to longer-term improvements in whole muscle size/function and whole body functionality.

Procedures:

All of the procedures and interventions on volunteers recruited for these studies are carried out solely for research purposes, as none are part of standard therapy in TKA patients. We will describe procedures that will be performed for each of the Aims.

Aim 1

Primary outcomes, which will be assessed at baseline and 5 wk post-intervention, include: skeletal muscle fiber cross-sectional area (CSA) and function, mitochondrial content, morphology and function and weight-bearing activity. Secondary outcomes include: whole muscle size/function and accelerometry. Procedures that will be performed on volunteers to obtain these primary and secondary outcome measures are described below.

Pre-surgery testing

Percutaneous skeletal muscle biopsy of the vastus lateralis (VL) will be performed on the leg scheduled to undergo TKA, per procedures used by our research group in a range of patient populations, including knee OA patients (1, 2). Tissue will be proportioned for mechanical (single fiber function), immunohistochemical (IHC), mitochondrial functional (oxygen consumption rate and hydrogen peroxide production) and electron microscopy (EM) measurements, with remaining tissue frozen in liquid N₂. The VL was chosen because of its importance in determining functional disability (3) and its structural and functional adaptations to TKA (4). The following measures will be assessed from muscle tissue.

Single fiber function will be assessed on segments of chemically-skinned muscle fibers, as used routinely by our lab. Cellular function will be measured on chemically-skinned, fiber segments, including force, velocity and power, as described by us (1) and molecular function (myosin-actin cross-bridge kinetics/mechanics) by sinusoidal analysis, as pioneered in human skeletal muscle by our lab (5). These measures will be available on the most abundant fiber types: MHC I, IIA and IIX (>90% of fibers in cancer patients (6)).

Single fiber cross-sectional area (CSA) will be measured by IHC, as described (1), with the addition of MHC IIA and IIX antibodies to delineate MHC II sub-types, as described (7), as these comprise the majority of fibers (MHC I, IIA, IIX; >90%) in cancer patients (2).

Mitochondrial content/morphology (sub-sarcolemmal and intermyofibrillar: % content, size, # per unit area/sarcolemmal length) and myofibrillar ultrastructure (myofibrillar % area, A-band length) will also be assessed by EM, as described by us (2, 6).

Accelerometry will be performed (5 d each): at baseline and ~weekly throughout the 5 week intervention, as described (12). This will be accomplished using an Actigraph waist-worn accelerometer.

Thigh muscle size and body composition will be measured, as described (13), to track changes in body composition and quadriceps muscle CSA by CT to characterize differential changes between legs, as described (2).

Thigh muscle function will be assessed by isokinetic/isometric dynamometry, as described (12), to characterize changes in whole muscle function (isometric: 70°; isokinetic: 60 and 180 °/sec), adjusted for quadriceps CSA, with central neural activation assessed by the interpolation technique, as described by us (14).

Whole body function will be assessed using the 30 second sit-to-stand test, timed up and go (TUG), stair climb (SCT) (16) and the Short Physical Performance Battery (SPPB) (17, 18), as described by us (19, 20).

Blood samples will be taken to examine circulating factors that may contribute to muscle atrophy and/or dysfunction.

Questionnaires will consist of the Western Ontario and McMaster Universities Arthritis Index (WOMAC) and Medical Outcomes Short Form (SF-36; Appendix 1) form to assess the symptom severity of the volunteer's knee OA, as well as their functional status and quality of life to be used as basic data to characterize the cohort so that, upon publication, readers can assess the external validity of our cohort.

NMES

NMES will be conducted on the quadriceps of the operative leg using a portable stimulation device (Empi Continuum; DJO Global), starting within 48-72 hrs of surgery, as described by us (21), and used in our preliminary studies at UVM (CHRMS 12-184). Briefly, the operative leg will be immobilized on a support board at a neutral angle (30°) or using a knee positioning bolster and ankle weight, with electrodes affixed to the anterior surface of the thigh. Symmetrical, biphasic pulses (400 µs duration at 50 Hz) will be used, with a duty cycle of 25% (10 s on, 30 s off), with patient-selected stimulation intensity to cause visible contractions below pain threshold. NMES sessions will occur 5 d/week, twice daily for 45 min (5 min warm-up) for 5 wks. Our prior trial (21) had excellent compliance, with 91 ± 2% of sessions completed at 5 weeks post-TKA, with compliance not related to age (P>0.5) or number of comorbidities (P>0.5). Studies utilizing muscle biopsies have yielded a similarly high compliance with

NMES (93 ±4%). Thus, we have assumed an attrition rate of 10% due to non-compliance. To track the NMES dose, volunteers will self-report device intensity (mA), as well as knee pain (see Appendix 2), with reports reviewed weekly by the study coordinator. Compliance will be confirmed using the compliance monitoring feature built-in to the device software and we will measure NMES dose (% pre-surgery MVIC) directly at 5 weeks post-TKA, as described (22).

Control

Volunteers randomized to the control group will not receive an NMES device and will be instructed to not undertake any structured exercise regimen outside of standard post-TKA rehabilitation. Controls will receive weekly phone calls to check on their rehabilitation and to standardize interaction with study personnel to the NMES group and will record knee pain similar to volunteers in the NMES group. We chose not to utilize a sham control NMES intervention (eg, electrical stimulation below the threshold to elicit muscle contraction) to mitigate the possibility that patients will increase stimulation intensities sufficient to produce muscle contractions if there is perceived benefit. Rigorous control over who receives NMES was considered preferable to controlling for any effects of sub-threshold, cutaneous electrical stimulation.

5 week Post-surgery testing will be identical to pre-surgery testing, as described above. The only addition to the pre-surgery regimen will be the use of NMES during strength testing in order to assess the intensity of muscle contraction elicited by the NMES stimulus, as described by us (22). Post-training muscle biopsies will be performed ≥3 following strength testing or the last bout of training to eliminate any residual effects, as described by us (23).

6 month Post-surgery testing will include whole muscle strength testing, body composition analysis and whole body functional assessments. The purpose of these assessments is not to assess whether NMES is effective at improving longer-term functional recovery, as our co-l's research has demonstrated (21), but instead to determine whether the effects of NMES to mitigate muscle atrophy and dysfunction during the early, post-surgical period predicts longer-term improvements in function.

2 week Post-surgery testing will be optional. Volunteers can opt in/out of testing at this time point. The primary purpose of testing at 2 weeks post-surgery is to obtain data at a mid-point between surgery and the 5 week time point to better define potential mechanisms contributing to muscle atrophy and contractile dysfunction. As with 5 week post-surgery testing, the contractile response to the NMES stimulus will be assessed during strength testing. The only omission will be contractile function measurements on single muscle fibers.

References cited above:

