For Aim 2, pre- and 5 wk post-surgery data will be compared between volunteers randomized to NMES and control interventions. Our primary analysis will assess treatment effects (group X time interaction) on muscle structural and functional variables. Primary outcomes are identical to Aim 1 and will be similarly evaluated using a general linear mixed model, as described above, with group (NMES vs. control) and time (pre vs. 5wks post-TKA) as between- and within-subject factors, respectively. Potential confounding factors will be compared between groups and factors that differ can be included into the model as level 2 covariates. We assume that dropouts will be random, but will examine whether they differ from volunteers completing the study. Moreover, we can conduct sensitivity analysis on dropouts, assuming the most and least conservative responses, to assess their impact on study outcomes. Additionally, we can include sex as an additional effect in these models to determine if NMES effects differ by sex. In secondary analyses, we will also examine the effect of treatment on whole muscle/body functional measures. If there are effects of NMES to maintain whole muscle/body functionality at 5 weeks, we will examine whether changes in single fiber structural or functional outcomes partially or completely mediate whole muscle/body functional improvements with NMES using mediation analysis.

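### The SAP's covariate rule for Aim 2 is not limited to variables measured before randomisation, so post-surgical activity, which NMES may change, could enter the primary model and bias the treatment effect in either direction

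*Protocol*

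**What the plan says.** **Protocol.** Methods and Procedures says that accelerometry across the five post-surgical weeks "will monitor variation in physical activity between groups". The description of pre-surgery testing gives the schedule: "at baseline and ~weekly throughout the 5 week intervention". Only the baseline recording therefore precedes randomisation.

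The outcome list under Procedures, Aim 1, ends its primary outcomes with "mitochondrial content, morphology and function and weight-bearing activity". The next sentence reads "Secondary outcomes include: whole muscle size/function and accelerometry". Both labels refer to one measurement, since Methods and Procedures describes "accelerometry to assess habitual weight-bearing activity level".

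**SAP.** For Aim 2: "Our primary analysis will assess treatment effects (group X time interaction) on muscle structural and functional variables". The primary outcomes are those of Aim 1: fiber CSA, tension and velocity for MHC I and IIA fibers, and IMF and SS mitochondrial content. Activity is not among them, and the SAP does not say how it will be analysed. The covariate rule is "Potential confounding factors will be compared between groups and factors that differ can be included into the model as level 2 covariates". The SAP gives no list of factors, no criterion for a difference and no time limit on when a factor must have been measured.

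**The concern.** In a randomised comparison, a variable measured after allocation is not a confounder of the treatment effect. If treatment can change it, a difference between arms may itself be an effect of treatment. Conditioning on it then moves the estimate away from the total effect of NMES, which is what the group by time comparison is meant to capture.

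The protocol's own account puts activity on a plausible causal path. It reports that earlier NMES work lessened strength and function losses. Its device section says that disuse, arising partly from weakness, causes fiber atrophy and mitochondrial loss. NMES could therefore raise activity and so help preserve fibers. It could also lower activity if sessions displace time on the feet. Pain is named as a further cause of disuse; if it also affects muscle by other routes, conditioning on activity adds bias of unknown sign.

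The rule comes into play when arms differ, so it is most likely to admit activity when NMES has changed it most.

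**Working it through.** **Inputs from the documents.** 1:1 allocation, 32 per group, 25% attrition, 24 per group completing. Check: 24 / (1 − 0.25) = 32, which reproduces the protocol's figure and is not in dispute.

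**Assumed inputs.** The documents give no alpha, power, effect size or SD. For illustration: two-sided 0.05, 80% power and standardised effects. The matching total effect at 24 per group is (1.96 + 0.84) × √(2/24) ≈ 0.81 SD. Let *a* be the NMES effect on activity in SD, and *b* the slope of muscle change on activity, with *b* > 0 meaning that activity protects muscle.

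**Step 1: how often the rule would admit activity.** If a difference means p < 0.05 with 24 per group, the chance is about 18% for *a* = 0.3, 41% for *a* = 0.5 and 79% for *a* = 0.8.

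**Step 2: what adjustment does when it acts on the change.** Adjusted effect = total effect − *a* × *b*. Power after adjustment uses SE = √(1 − b²) × √(2/24) / √(1 − r²), with r² = (a²/4) / (1 + a²/4).

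| *a* | *b* | Adjusted effect (SD) | Share removed | Power (80% unadjusted) |
|---|---|---|---|---|
| 0.3 | 0.2 | 0.81 − 0.06 = 0.75 | 7% | 75% |
| 0.5 | 0.4 | 0.81 − 0.20 = 0.61 | 25% | 61% |
| 0.8 | 0.6 | 0.81 − 0.48 = 0.33 | 59% | 26% |

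If NMES lowers activity, the sign reverses: *a* = −0.5 and *b* = 0.4 give 0.81 + 0.20 = 1.01.

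**Step 3: does the model form matter?** Simulated with 200 replicates, total effect 0.81, *a* = 0.5, *b* = 0.4 and complete pre/post data (Monte Carlo error about 0.02):

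| Model | NMES effect |
|---|---|
| Group by time, unadjusted | 0.80 |
| Plus activity as a time-constant main effect | 0.80 |
| Plus activity by time | 0.60 |
| Baseline-adjusted, without activity | 0.80 |
| Baseline-adjusted, with activity | 0.60 |

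A separate simulation entered activity as a time-varying covariate. The group by time estimate moved from 0.81 to 0.59 when NMES raised activity by 0.5 SD, and from 0.78 to 0.98 when NMES lowered it. Those shifts of −0.22 and +0.20 are close to the 0.20 in Step 2.

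The time-constant term is harmless because group by time is a within-person contrast, from which a value fixed over time cancels. The other forms do not cancel.

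**The case against.** The strongest reply is that the SAP calls these level 2 covariates and describes level 2 as whole-muscle or person-level. Read as a single value per person entered as a main effect, activity would leave the primary estimate essentially unchanged. That stands for this form with complete data. It does not close the gap: activity is measured at baseline and during follow-up, the SAP's two levels (fiber and person) include no separate visit level, and nothing rules out a per-visit value, an interaction with time or a baseline-adjusted model.

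It is also fair that the SAP never names activity, says only that factors can be included, and gives the baseline value as its one covariate example. The adjustment is therefore permitted, not planned. The example is followed by an open-ended etc. and belongs to Aim 1, so it restricts nothing in Aim 2.

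Some stronger readings are tempting but not supported:

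- **That the protocol contradicts itself by making activity both an outcome and a monitored difference.** A measure can be both. Monitoring may simply check conduct, since the Control section tells controls not to take up structured exercise beyond standard rehabilitation.
- **That NMES benefit would necessarily be adjusted away.** The bias can run in either direction.
- **That session time shows activity must fall.** Sessions total 2 × 45 min × 5 = 450 min, or 7.5 h a week, but the documents do not say whether this replaces weight-bearing activity or rest. The NMES section also allows a bolster with ankle weight in place of the support board.

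**Conclusion.** The concern holds as a gap in the covariate rule. Following the SAP as written could condition the primary Aim 2 comparison on a variable measured after randomisation that NMES may change. The documents do not show that this adjustment is intended.

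The consequence depends on three open matters: whether activity is chosen, how it enters the model, and how far NMES changes it. If it enters in a form that acts on the change and activity protects muscle, the NMES effect is understated when NMES raises activity and overstated when NMES lowers it. The size cannot be derived from the documents, and the figures above are illustrations on assumed inputs. A reader might want to state a fixed percentage loss, but no figure in the plan supports one. The SAP's sensitivity analysis concerns dropouts and would not reveal this bias.

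A related inconsistency is real: the protocol lists weight-bearing activity as primary and accelerometry as secondary, though they are the same measurement, while the SAP's primary list omits activity.

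**What to change.** In the Aim 2 section of the SAP, replace the factors-that-differ rule with a prespecified list of pre-randomisation covariates. Suitable candidates are the randomisation factors (age, BMI, sex and surgeon) and baseline values, including baseline accelerometry. State the form in which each enters the model.

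Add that accelerometry from weeks 1-5 is analysed only as an outcome or candidate mediator and reported by arm, and that any activity-adjusted treatment effect is exploratory. This fits the mediation analyses the SAP already plans.

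Give activity one outcome status, and make the protocol's Aim 1 outcome list and the SAP's primary list agree.

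The cost is a few sentences in the SAP and a matching edit to the protocol, with no new data or visits.
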